13.4 Sample Size and Accrual Rate

Phase I: In general, the total sample size will depend on the number of dose levels evaluated to determine the RP2D. Assuming the highest dose tested is well tolerated (3 patients treated on dose levels 1 (20mg) and 3 (40mg); 6 patients treated on assumed MTD -dose level 5 (60mg), the phase I portion of the study would enroll and treat 12 patients. The expected sample size is 12-18 patients, allowing for 6 patients to replace inevaluable/ineligible patients. A maximum of 36 participants could be treated if 6 participants are treated at each dose level. A minimum of 6 patients could be treated if leflunomide is not well tolerated.

Assuming one patient is enrolled each month, accrual is expected to be completed in 12-18 months for the phase I portion. When the phase II portion begins, it is anticipated that the accrual rate will increase. This is a priority trial and the initiation of the phase II portion is likely to coincide with the end of other trials, increasing the pool of potential candidates. Therefore, we estimate a rate of 2 patients per month for the phase II portion, for an accrual time of 17 months. The expected follow-up time is 24 months, for an estimated maximum total study duration of (18+17+24) 59 months, or roughly five years. In the event that participants are receiving treatment at the end of the study, additional options for continuation, such as compassionate use, will be considered. With ~150 relapsed or relapsed/refractory MM patients treated at COH per year, we do not expect any problems accruing the required patient numbers for both phases of the clinical trial within 29-35 months from start of study, and therefore both phases of the clinical trial will be conducted solely at COH.

13.5 Statistical Analysis Plan

Patient demographic and baseline characteristics, including age, gender, medical history, and prior therapy, will be summarized using descriptive statistics. For continuous variables, descriptive statistics (number [n], mean, standard deviation, standard error, median (range) will be provided. For categorical variables, patient counts and percentages will be provided.

Analysis: Observed toxicities will be summarized, for all dose levels, in terms of type (organ affected or laboratory determination), severity, time of onset, duration, serum concentration of the active leflunomide metabolite, probable association with the study treatment and reversibility or outcome.

The overall response rate and clinical benefit response rate will be calculated, for the initial and sub-analysis for all dose levels; Clopper Pearson binomial 95% confidence intervals will be calculated for these estimates. As part of the initial analysis of response, the overall response rate (patients that have confirmed sCR/CR/VGPR or PR) and clinical benefit response rate (patients that have confirmed sCR/CR/VGPR/PR/MR or SD) will be calculated among all patients included in the study even if there are

protocol treatment deviations or if the patient is later determined to be ineligible. In addition, as part of the phase II anti-myeloma activity assessment, sub-analyses will be performed where participants will be considered evaluable for response if they are confirmed eligible, receive at least 75% of leflunomide during the first cycle of therapy and have their disease re-evaluated. Response rates will also be evaluated based on number/type of prior therapy(ies) and serum concentration of the leflunomide metabolite (μ g/mL). Time to response and survival will be estimated using the product-limit method of Kaplan and Meier.

Pharmacokinetics: Because serum concentration of the metabolite, teriflunomide (A77 1726), can be variable, and because some studies have found an association between serum concentration of this metabolite and RA response, samples will be collected throughout the study for analysis by the Analytical Pharmacology Core Facility (APCF) for an exploratory analysis relating metabolite levels to safety and efficacy outcomes. At the conclusion of the study, total and free teriflunomide levels will be summarized at 2- and 4-week sampling time points. Descriptive statistics will be used to characterize possible inter-patient variability and relationship to dose, toxicity and response for future studies, including guidance with respect to RP2D selection. Additional testing and analysis will be done on collected samples to assess, in an exploratory manner, the potential association between germline polymorphisms in the DHODH gene and either toxicity or response.

Pharmacogenomics: To evaluate the independent effect of germline polymorphisms, all models will be adjusted for risk factors known to be associated with outcomes studied (e.g., age, disease status). Multiple comparisons adjustment with false discovery rate (FDR) will be conducted, and variants with $FDR \leq 0.05$ will be considered significant. We will specifically look at *DHODH*, *CYP1A2* and *CYP2C19* gene polymorphisms and haplotypes identified in the literature that are associated with leflunomide response/toxicity in RA. Functional annotation of the variants will be performed using ANNOVAR. The major goal of this analysis is to identify potential SNPs that might affect the responsiveness of treatment, other than the miRNA/mRNA/methylation signature. Given the small sample size, we consider this analysis as exploratory and may not provide enough power to detect significant associations.

***Ex vivo* and molecular studies:** The IC50 values for teriflunomide in MM cells will be calculated using Prism software (GraphPad). These values will be used for correlation analysis to determine the strength and linearity of the relationship between the *ex vivo* response and the response characteristics *in vivo*. The results will also be compared to responses from cell lines.

For the studies combining teriflunomide with other agents *ex vivo*, combination Index (CI) values will be calculated using the CalcuSyn software program (Biosoft, Ferguson) to determine which of the compounds work synergistically, if any. A combination index of < 0.9 indicates synergism, whereas $CI = 0.9$ to 1.1 indicates additive effects. $CI > 1.1$ indicates antagonism. Isobogram diagrams will be generated that show the varying combination treatments and the ratio where maximal synergy is obtained.

The miRNA/mRNA expression profile and DNA methylation data will be used to identify the miRNA/mRNA and differential methylated regions (DMRs) that show significant differences between responders and non-responders after leflunomide treatment. For miRNA/RNA profiling, fold changes >3 with an FDR <0.05 will be considered significant. Assuming the dispersion of genes across replicates is 0.2 and minimum average expression is 10 reads per gene, 10 samples in each group (responder vs. non-responder) should have 89% power to detect a 3-fold difference between groups at an FDR level of 0.05.

The major goal of RNA-seq/miRNA-seq/RRBS-seq is to predict potential responders based on pre-treatment genomic profiling. A logistic regression-based algorithm with risk score formula described previously [46] will be used to build a classifier for response prediction. Differentially expressed miRNA/mRNA and DMRs together with other known clinical risk factors will be included in the

multivariable logistic regression model. The performance of the identified classifier will be evaluated with leave one out cross validation (LOOCV). Specifically, for each iteration -as part of a random selection process, one sample will be left out as the test sample; the remaining samples will be used to build a classifier, and the classifier will be used to predict the response status of the test sample. The sensitivity and specificity of the classifier will be calculated, as well as receiver operating characteristic (ROC) curve and area under the curve (AUC) to evaluate its accuracy.

Another goal of the genomic profiling is to identify potential new pathways to complement leflunomide treatment. We will compare the miRNA/mRNA/methylation profiles between responders and non-responders. Differentially expressed genes will be used to identify pathways that are activated in non-responders, which will provide insights into possible complementary therapy. Gene ontology (GO) and KEGG pathways will be analyzed using DAVID and GSEA. Pathways and GO that are activated in non-responders will be sorted by their multiple comparison adjusted p-value. Potential miRNA targets will be identified using TargetScan and the enrichment of GO and pathways will be identified as well. The NCI connectivity map, an online resource to predict therapeutic efficacy based on pathway based gene expression profiles, will also be explored to determine the complimentary therapeutic agents for leflunomide.

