The long half-life of the metabolite (about 2 weeks) affects management of patients taking leflunomide. A loading dose of 100 mg for 3 days is used to facilitate rapid attainment of steady state levels of M1. Without a loading dose, it is estimated that attainment of steady state concentrations would require nearly two months of dosing [22]. To eliminate the metabolite, a drug elimination procedure using cholestyramine is recommended. Cholestyramine, a bile acid sequestrant, fixes the metabolite, preventing reabsorption and expediting drug elimination. Without the drug elimination procedure, it may take up to 2 years to reach non-detectable plasma levels after stopping treatment with leflunomide [22].

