9.0 CORRELATIVE/SPECIAL STUDIES

9.1 Pharmacokinetics

All participants will undergo serial blood sampling to evaluate the steady-state systemic exposure to teriflunomide (A77 1726) the active metabolite of leflunomide. Pharmacokinetic sampling will consist of trough level monitoring throughout the entire period of active treatment with leflunomide.

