9.1.4 Pharmacokinetic Data Analysis

Non-compartmental pharmacokinetic analyses of teriflunomide (A77 1726) will be used to determine the average steady-state total and free teriflunomide trough concentration (C_{trough}). C_{trough} results will be summarized within and between participants using means and standard deviations.

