10.0 STUDY CALENDAR

Table 10 describes required procedures. All procedures may increase in frequency if clinically indicated or oriented following toxicity. Adjustments to the treatment cycle due to a hold in study agent are detailed in [Section 5.2](#).

Table 10.0 Study Activity Calendar

	Screening ^a	Cycle 1, 2, 3		Cycle 4+ ^d	End of Treatment ^e				Active Follow-Up ^j	Long Term Follow-Up ^k
		Day 1 ^b	Day 14 ^c		Day 0 ^f	Days 1-11 ^g	Day 14 ^h	Day 30 ⁱ		
Informed Consent ^l	X ^u									
Inclusion/Exclusion Criteria ^m	X									
Registration ⁿ	X ⁿ									
Medical history ^o	X									
Physical exam	X	X		X					X	
Vital signs ^p	X	X		X					X	
Adverse events assessment ^q		X	X	X	X	X			X	
Concomitant meds review	X	X		X	X				X	
ECOG status ^r	X	X		X					X	
Pregnancy test ^s	X									
TB antigen test ^t	X									
Hepatitis A, B, C testing	X ^u									
Pulmonary function test	X ^u									
Extramedullary disease survey ^v	X ^u			X ^w	X ^w				X ^w	X ^w
Skeletal survey	X ^u									
Clinical bone marrow aspiration/biopsy with research use of leftover samples	X ^{u,y}	X ^{y,z,aa}		X ^{y,z}	X ^{y,z}				X ^{y,z}	X ^{y,z}
Research bone marrow aspiration		X ^{bb}								
CBC with differential ^{cc}	X	X	X	X					X	X
Chemistry panel ^{dd}	X	X	X	X					X	X
Myeloma labs ^{ee}	X	X ^{kk}		X	X				X	X
Response assessment ^{ff}		X ^{aa}		X	X				X	X
Research blood samples ^{gg}		X	X	X	X					
Teriflunomide clinical testing ^{hh}				X		X ⁱⁱ	X ⁱⁱ			
Leflunomide administration ^{jj}		Daily								
Cholestyramine ^g					X ^g					
Survival										X ^k

a. All screening procedures to be performed within 21 days of start of study agent except informed consent, acute hepatitis panel, skeletal survey, bone marrow biopsy, and pulmonary lung function test which may occur within 30 days of start of treatment (footnote u) and except for registration which must occur within 7 days from start of treatment (footnote n).

- b. Day 1 assessments to be performed within 5 days (120 hours) prior to Day 1 drug (except footnote u for C1 only). Day 1 safety assessments must be resulted and reviewed prior to administration of agent for the cycle that is initiating. Screening assessments, if performed within this aforementioned time frame, may serve as C1D1 assessments. Note: items with footnote "aa" are not performed for C1D1; the windows for screening assessments still apply.
- c. Day 14 evaluations have +/- 3 day window.

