13.3 Study Design

13.3.1 Phase I Design

This single agent phase I dose-escalation trial is designed to determine the MTD and RP2D. The RP2D of leflunomide will generally be the MTD, but it may be less than the MTD based on a review of available data/cumulative toxicities. Extensive pharmacokinetic and pharmacodynamic studies are also incorporated into this protocol and may be helpful in determining the RP2D.

While the standard dose of leflunomide, 20mg daily, is FDA approved for continuous treatment of rheumatoid arthritis, leflunomide has been administered without an increase in the type, frequency or severity of adverse events at doses up to 40 mg/day in patients with Wegner's granulomatosis, and up to 60mg/day in a subset of patients with polyoma BK neuropathy to achieve targeted therapeutic levels. We will therefore attempt to escalate the dose of leflunomide to three times that approved for RA using a modified rolling six dose-escalation/ de-escalation/expansion design, a more conservative version of the rolling six design of Skolnik, et al.[1]. The starting dose of leflunomide is 20mg daily, with the intention to test up to 60mg daily. Escalation will proceed in increments of 20mg/day (odd numbered dose levels); de-escalation will proceed in decrements of 10mg/day.

Table 13.3.1 Dose Levels

Dose Level	Leflunomide Dose*
-1	10 mg PO daily
1	20 mg PO daily
2	30 mg PO daily
3	40 mg PO daily
4	50 mg PO daily
5	60 mg PO daily

*NOTE: Leflunomide is administered with a loading dose of 100 mg for the 1st three doses.

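### Does the plan need to define which teriflunomide troughs count as steady state?

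*Combined protocol and SAP*

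**What the plan says.** Section 9.1 provides for serial blood sampling "to evaluate the steady-state systemic exposure to teriflunomide", by troughs taken over the whole of active treatment. Section 9.1.4 adds that non-compartmental analyses "will be used to determine the average steady-state total and free teriflunomide trough concentration", summarised within and between participants by means and standard deviations. No section gives a first qualifying visit, a minimum number of samples, or a rule for samples taken after a hold or dose change.

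Section 13.5, under Pharmacokinetics, states that at the end of the study "total and free teriflunomide levels will be summarized at 2- and 4-week sampling time points". Descriptive statistics then relate levels to dose, toxicity and response. The same section says: "Response rates will also be evaluated based on number/type of prior therapy(ies) and serum concentration of the leflunomide metabolite".

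Table 10 marks the row "Research blood samples" at Day 1 and Day 14 of cycles 1 to 3, at each cycle from cycle 4 on, and at End of Treatment Day 0.

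On the pharmacology, section 2.2 says: "The long half-life of the metabolite (about 2 weeks) affects management of patients taking leflunomide". It adds that without a loading dose "it is estimated that attainment of steady state concentrations would require nearly two months of dosing". The note to Table 13.3.1 reads "Leflunomide is administered with a loading dose of 100 mg for the 1st three doses" and applies to every dose level.

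**The concern.** If the 2- and 4-week time points are treatment weeks 2 and 4, and if those values stood in for the steady-state trough of section 9.1.4, exposure would be understated. The understatement would grow with dose, because the same 3 x 100 mg load covers a smaller share of steady state as the maintenance dose rises. Proportional kinetics would then look less than proportional, and a concentration range linked to response or toxicity would be set too low. Section 2.6 mentions exposure-targeted studies as a possible sequel, so the absolute values have a use beyond this trial.

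The other reading leaves a question too. If all troughs were averaged over each patient's stay, early leavers would appear less exposed simply because they left before accumulation was complete.

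**Working it through.** **Inputs.** Half-life about 14 days (sections 2.2 and 8.1.4). Load 100 mg on days 1 to 3 at every level (section 5.5.1). Maintenance doses from Table 13.3.1; note jj to Table 10 gives 20 or 10 mg instead, and those passages must be reconciled, but that is a separate matter. Cycle length 28 days (section 5.2), so cycle 2 day 1 is day 29, cycle 2 day 14 is day 42 and cycle 3 day 1 is day 57. Linear one-compartment kinetics, immediate input and full adherence are assumptions; the documents give no model.

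**The plan's own figure.** Without a load, the share of steady state at day t is 1 − 0.5^(t/14). At 56 days this is 93.8% and at 60 days 94.9%, which agrees with the statement of nearly two months.

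**With the load.** Let r = 0.5^(1/14) = 0.9517. Before the day 4 dose the share is F(4) = (100/D)(1 − r³) = 13.80/D with D in mg, or 69%, 35% and 23% at 20, 40 and 60 mg. After that, F(d) = 1 − (1 − F(4)) r^(d−4). For 60 mg on day 29: 1 − 0.770 × 0.290 = 0.777.

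| Pre-dose trough, % of steady state | 20 mg | 40 mg | 60 mg |
|---|---|---|---|
| Day 14 | 81 | 60 | 53 |
| Day 29 (cycle 2 day 1) | 91 | 81 | 78 |
| Day 42 (cycle 2 day 14) | 95 | 90 | 88 |
| Day 57 (cycle 3 day 1) | 98 | 95 | 94 |
| Day 85 (cycle 4 day 1) | 99 | 99 | 99 |

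For half-lives of 10 to 18 days, the 60 mg values are 66% to 44% on day 14 and 88% to 69% on day 29.

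**Dose ratio.** The 60:20 mg trough ratio is 3 × 0.531/0.811 = 1.96 on day 14, 3 × 0.777/0.910 = 2.56 on day 29 and 3 × 0.944/0.978 = 2.90 on day 57, against 3.0 at steady state.

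**Phase I precision.** With a CV of 50% the log SD is √ln(1.25) = 0.472. For 3 patients at 20 mg and 6 at 60 mg, the SE of the log ratio is 0.472 × √(1/3 + 1/6) = 0.334. The gap ln(3.0/2.56) = 0.159 is about half an SE.

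**Phase II precision.** The week 4 shortfall factors are 1.10, 1.23 and 1.29 at 20, 40 and 60 mg. The 95% limits on a geometric mean are a factor of exp(1.96 × log SD/√n). The spread reported in section 2.2 at 20 mg (mean 42, SD 35 mg/l) is a CV of 35/42 = 83%, log SD √ln(1.694) = 0.726.

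| | n = 39 | n = 19 |
|---|---|---|
| CV 50% | 1.16 | 1.24 |
| CV 83% | 1.26 | 1.39 |

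The 40 mg shortfall lies outside these limits only for 39 patients at a CV of 50%. The 60 mg shortfall is inside them for 19 patients at a CV of 83%. Section 13.3 puts the chance of stopping at 19 patients at 0.68 if the true response rate is the disappointing 15%.

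These limits use steady-state spread. In a simulation with a clearance CV of 50% and an assumed volume CV of 20% to 30%, the week 4 spread at 60 mg is narrower, a CV of 28% to 31%. At 31% (log SD 0.303) the limits are 1.10 for n = 39 and 1.15 for n = 19, and a shortfall of 1.29 would exceed both. The comparison therefore turns on the spread assumed and does not settle the point.

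**Ranking.** In that simulation, over 20 to 60 mg, the rank correlation of the trough with the patient's own steady state is 0.63 to 0.85 on day 14 and 0.88 to 0.97 on day 29.

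**The case for a change.** The best case for amending the text is that both clinical pharmacology objectives rest on this exposure measure, and that section 13.3.1 allows pharmacokinetics to inform the choice of phase II dose. A rule fixed in advance would also prevent a later choice among metrics. The averaging problem is real in principle. A typical 60 mg patient who leaves after cycle 2 day 1 would average (53 + 78)/2 = 65% of steady state, and one who stays to cycle 6 day 1 would average 89%, a ratio of 1.35 from time on treatment alone. Since patients stop for progression or toxicity (section 5.8), that artefact would follow outcome.

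Part of this stands. The qualifying visits are not named and the 2- and 4-week phrase is ambiguous. But no section proposes averaging every trough, and section 13.5 does not equate its 2- and 4-week levels with the quantity in section 9.1.4. Summarising levels at those weeks is a legitimate description of exposure at those weeks. Its wording also fits the calendar, which runs two-weekly for three cycles and four-weekly after that.

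The material for a proper steady-state estimate is already collected. Patients who leave before cycle 3 are not limited to one week 4 value: depending on when they stop, they may also have day 14, day 42 and End of Treatment Day 0 samples. More elaborate rules, such as a fixed exclusion period after holds or a time-varying trough for toxicity, are reasonable preferences. They have a cost as well: restricting to late troughs leaves a smaller, selected group.

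**Conclusion.** No change to the plan follows. The calculation is sound: under the stated model, week 2 and week 4 troughs at 60 mg are about 53% and 78% of steady state and should not be labelled steady state in a report. But no stated rule labels them so. What is missing is a definition that a pharmacokinetic analyst would supply from the half-life printed in section 2.2, using samples that Table 10 already schedules; by day 57 a typical patient is within about 6% of steady state even at 60 mg.

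The stakes are limited. The work is exploratory and descriptive, no test, response threshold or dose-escalation rule uses it, and week 4 ranking of patients is largely kept. The phase I dose-ratio distortion is about half a standard error. Whether the phase II shortfall exceeds sampling error depends on the spread and sample size assumed.

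The percentages rest on linear kinetics, a 14-day half-life and full adherence, and describe a typical patient. Naming the visits in the analysis report, with levels shown by visit, would be enough.

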9.3 Pharmacogenomics

All participants will undergo genetic studies to evaluate germline genetic polymorphisms in the coding exome. The potential association between germline polymorphisms in CYP1A2, CYP2C19, and DHODH and either toxicity or response will be analyzed. CYP1A2 and CYP2C19 are major leflunomide metabolic enzymes and DHODH is the main molecular target of leflunomide

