9.3.2 Gene Sequencing Data Analysis

Gene sequences provided by the IGC will be assessed for gene polymorphisms identified in the literature [20, 21] associated with leflunomide response in RA.

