⁺: Although under this scenario escalating to the next higher dose level is suggested, additional patients can be accrued to the current level -up to n=6 patients.
^{**}: Patients treated on a higher dose will have their treatment modified to the dose below the dose level with 2 DLTs, if pending patients have DLT.

Phase II Design

Following completion of the phase I portion of the study and identification of the RP2D, the phase II portion of the study will be initiated. Recent studies evaluating daratumumab, a CD38 monoclonal antibody, as monotherapy for relapsed/refractory multiple myeloma were recently published [39, 40] and have led to FDA approval of this agent. One study included patients with relapsed multiple myeloma treated with at least three lines of therapy while the other included patients treated with at least two prior lines of treatment. Treatment with daratumumab as a single agent lead to an overall response rate of 29.2% and 36% respectively in each of these studies. In both studies, the agent investigated was well tolerated but required IV dosing once weekly for 8 doses, followed by twice-monthly doses for 8 doses and then monthly thereafter. We suspect leflunomide to be similarly well tolerated but with a more convenient dosing schedule. Because we are including patients who have received at least three prior lines of treatment, we will target an overall response rate of 30% for the phase II portion of the study.

This single-center, single arm phase II trial will implement a Simon Two-Stage Optimal Design [2, 3]. to evaluate the anti-myeloma activity of leflunomide, when given as a single agent, as assessed by overall response rate (ORR), in patients with relapsed or relapsed/refractory MM. The phase II portion of the study is expected to enroll a minimum of 19 and a maximum of 39 patients. The sample size is based on the desire to discriminate a promising ORR of 30% from a disappointing response rate of 15% using a type I error rate of 0.10 and power of 80%.

At stage 1, 19 patients will be entered on the study. If ≤ 3 responses are seen, the study will be terminated. If at least 4 patients achieve response, the trial will continue to the second stage. The 6 patients treated at the RP2D in the phase I portion will be evaluated as part of this phase II group. The probability of early stopping after the first stage is 0.68.

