At stage 2, 20 additional patients will be entered. At the end of stage 2, if 9 or more patients respond, leflunomide -as single agent therapy, will be considered worthy of further study. If ≤ 8 patients respond further investigation is not warranted.

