APPENDIX B. DETAILED METHODS FOR PHARMACOGENOMIC, EX VIVO, AND MOLECULAR STUDIES

This is a description of the detailed analytical methods at the time of protocol submission. Any changes to the procedures will be stored in the laboratory manual of procedures/standard operating procedures or in the laboratory research notes.

Pharmacogenomics

The extracted DNA material will then be sent to the Integrative Genomics Core (IGC; Director, [name]) for sequencing. The DNA samples will be fragmented into 200 bp, and a pre-capture library will be generated following Illumina's recommended protocol. Agilent SureSelect Human all exon V6 probes will be used to capture the coding exome. The captured library will be sequenced on an Illumina Hiseq 2500 for paired-end 100 bp sequencing for a minimum of 100x coverage. The paired-end sequences will be aligned to the human genome (hg38) using Novoalign. Only reads aligned to a unique genomic location will be kept for further analysis. The aligned reads will be piled up using Samtools. Variants (SNPs and short indels) will be identified using VarScan. The quality of variants will be assessed by the concordance of variants to the dbSNP database. The prognostic significance of germline polymorphisms on toxicity risk/response will be analyzed using univariate and multivariable logistic regression. To evaluate the independent effect of germline polymorphisms, all models will be adjusted for risk factors known to be associated with outcomes studied (e.g., age, disease status). Multiple comparisons adjustment with false discovery rate (FDR) will be conducted, and variants with $FDR \leq 0.05$ will be considered significant. We will specifically look at *DHODH*, *CYP1A2* and *CYP2C19* gene polymorphisms and haplotypes identified in the literature that are associated with leflunomide response/toxicity in RA. Functional annotation of the variants will be performed using ANNOVAR. The major goal of this analysis is to identify potential SNPs that might affect the responsiveness of treatment, other than the miRNA/mRNA/methylation signature. Given the small sample size, we consider this analysis as exploratory and may not provide enough power to detect significant associations.

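### Germline-variant analysis: with 6 to 15 responders, ordinary logistic regression often has no finite estimate for low-frequency variants, and the FDR family is not defined

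*Combined protocol and SAP*

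**What the plan says.** The objective (Section 1.0) is to explore polymorphisms in CYP1A2, CYP2C19 and DHODH in relation to toxicity and response.

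- **What is sequenced.** Section 9.3 has all participants undergo genetic studies "to evaluate germline genetic polymorphisms in the coding exome". It then names only the three genes as associations to be analysed. Appendix B describes exome capture and the calling of SNPs and short indels.
- **What is assessed.** Section 9.3.2: "Gene sequences provided by the IGC will be assessed for gene polymorphisms identified in the literature", citing references 20 and 21, both on DHODH.
- **Model.** Appendix B says that toxicity and response "will be analyzed using univariate and multivariable logistic regression". Section 13.5 adds: "To evaluate the independent effect of germline polymorphisms, all models will be adjusted for risk factors known to be associated with outcomes studied". Age and disease status are given as examples, so the covariate list is open.
- **Multiplicity.** Variants with an FDR of at most 0.05 count as significant. The family is not stated. Section 13.5 singles out the three genes but gives the main goal more broadly, as finding SNPs that may affect response.
- **Caveat.** The analysis is called exploratory and possibly underpowered.

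The plan gives no estimation method, no test (Wald, likelihood ratio or exact), no provision for separation and no minimum carrier count.

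**The concern.** Two gaps matter here.

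First, a logistic model has no finite maximum-likelihood odds ratio when the variant separates the outcome, for example when no carrier responds. Software then returns an arbitrary large number with a huge standard error, and a Wald p-value near 1 can follow even if the association is perfect. A table that mixes such output with real estimates is of little use to a later study.

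Second, the FDR family decides how strict the threshold is. If it is left open, the analyst can choose between a handful of candidate tests and many thousands of exome tests after seeing the data.

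The stake is a stated exploratory objective. No trial decision depends on it.

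**Working it through.** **1. Design figures that fix the number of responders.** The Phase II Design text gives: "The phase II portion of the study is expected to enroll a minimum of 19 and a maximum of 39 patients". The aim is to "discriminate a promising ORR of 30% from a disappointing response rate of 15% using a type I error rate of 0.10". The stage 1 rule is: "If ≤ 3 responses are seen, the study will be terminated". The success rule is: "At the end of stage 2, if 9 or more patients respond". Exact binomial calculation gives P(X ≤ 3 | n = 19, p = 0.15) = 0.684 against the stated 0.68, type I error 0.097 and power 0.803. The design reproduces, so its N and rates can be used.

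**2. Expected responders.**
- Phase II set: 39 × 0.15 = 5.85 and 39 × 0.30 = 11.7, so about 6 to 12.
- All sequenced patients: 12 to 18 in phase I plus 33 new in phase II (Section 5.4) is 45 to 51. Then 45 × 0.15 = 6.75 and 51 × 0.30 = 15.3, so about 7 to 15.
- If stage 1 stops the trial, at most 3 of the 19 respond.
- A variant plus two covariates is three slopes, so 6/3 = 2 to 12/3 = 4 responders per slope at n = 39.

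**3. How often no finite estimate exists.** For a variant unrelated to response, with carrier proportion q and response rate p, the chance that no carrier responds is (1 − qp)^n. For q = 0.10, p = 0.15, n = 39 this is 0.985^39 = 0.55. This is the main route to separation. The table compares it with simulated models holding the variant, a continuous and a binary covariate (n = 39, most runs checked for separation by linear programming; ranges are over repeated runs). Carrier proportions are assumptions, since the documents give none.

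| Carriers | (1 − 0.15q)^39 | Simulated, ORR 15% | (1 − 0.30q)^39 | Simulated, ORR 30% |
|---|---|---|---|---|
| 10% | 0.55 | 58-62% | 0.30 | 31-33% |
| 20% | 0.30 | 34-40% | 0.09 | 9-12% |
| 30% | 0.17 | about 22% | 0.03 | about 3% |
| 40% | 0.09 | about 17% | 0.01 | below 1% |

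For rare variants (allele frequency 0.01) the simulated share is 92% with 6 responders and 83% with 12. Using 51 patients helps but does not remove the problem: 0.985^51 = 0.46 and 0.97^51 = 0.21 at 10% carriers.

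**4. Role of the covariates.** The same simulation with and without adjustment gives 57.5% v 54.3% (10% carriers, ORR 15%), 31.3% v 31.2% (10%, ORR 30%), 34.8% v 31.3% (20%, ORR 15%) and 12.2% v 11.8% (20%, ORR 30%). Adjustment adds up to about 3 percentage points. Sparse carriers among few responders explain the rest.

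**5. Effect of the FDR family.** For a single true signal the Benjamini-Hochberg threshold is 0.05/m. Assume 30% carriers and response of 60% in carriers v 15% in others. The overall rate is 0.3 × 0.60 + 0.7 × 0.15 = 0.285, and the odds ratio is (0.60/0.40)/(0.15/0.85) = 8.5. Power of Fisher's exact test:

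| n | m = 6 (0.0083) | m = 20,000 (0.0000025) |
|---|---|---|
| 39 | 0.50 | 0.01 |
| 51 | 0.66 | 0.04 |

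The values of m are assumptions. With adjusted likelihood-ratio tests at an odds ratio of 5 (n = 39, 20-40% carriers, ORR 15-30%), power is 25-46% for m = 3 and 0.1-0.7% for m = 20,000.

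**6. Effect of the unstated test.** At n = 39, ORR 15%, 40% carriers, odds ratio 10 and threshold 0.05/3, power is 0.37 for Fisher's exact test and 0.10 for the adjusted Wald test.

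**The case against.** The strongest reply has four parts.

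- **The family may well be the candidates.** Sections 1.0, 9.3 and 9.3.2 all point to three genes or to literature polymorphisms, and exome capture may simply be the laboratory platform. This stands. A reader might infer that the plan applies FDR across the exome, but no sentence sets that family. The power loss in step 5 is conditional on that reading, and the defect is that the family is undefined.
- **Maximum likelihood and Wald tests are not named.** This also stands. The text says only logistic regression. Without a penalised or exact variant, ordinary fitting is the default reading, so the result is conditional on it.
- **The covariate adjustment is not the culprit.** The adjustment sentence tempts one to blame the covariates, but step 4 shows that they contribute little. Limiting them is sensible with 2 to 4 responders per slope, yet it would not cure separation.
- **Sample size is the real limit, and the plan says so.** This is largely right. For 35% v 15% (odds ratio about 3, 30% carriers, n = 39), exact-test power is about 7% with 6 tests and 22% with no correction. But the caveat concerns power. It does not cover models without a finite estimate, or a family that could be chosen afterwards.

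It is also tempting to say that the CYP candidates have no source. Section 2.5 cites references 32-34 for CYP1A2, CYP2C19 and DHODH, so Section 9.3.2 only lacks a cross-reference.

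**Conclusion.** The concern holds in a limited form and is minor. At n = 39, if logistic regression is fitted in the ordinary way, variants with 10-20% carriers have no finite estimate in roughly 30-60% of data sets at a 15% response rate and 10-30% at 30%. For variants with 30-40% carriers the share is about 17-23% at 15% and at most about 3% at 30%. The FDR family is undefined. Read as exome-wide with 20,000 tests, it would cut candidate power from about 0.5 to 0.01-0.02 for response of 60% v 15%. Read as candidate-only, it would not.

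These figures rest on assumed carrier proportions, assumed numbers of tests and the response endpoint. Toxicity event counts are not stated and were not assessed. The documents do not support the stronger conclusion that the candidate-gene question cannot be answered at all: that would need both the exome-wide reading and low-frequency candidates, and neither is established.

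**What to change.** In Sections 13.5 and 9.3.2 and in Appendix B:

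1. Replace ordinary logistic regression by Firth-penalised logistic regression with profile-likelihood intervals, or by exact tests. Firth estimates stay finite under separation. Report estimates with intervals as well as significance.
2. Name a short, closed list of covariates in place of the open examples.
3. Set a minimum carrier count for modelling, chosen before the outcome data are seen, and only tabulate variants below it.
4. List the literature polymorphisms in DHODH, CYP1A2 and CYP2C19 (references 20, 21 and 32-34) before analysis, and control FDR at 0.05 within that list as a separate family.
5. Report all other exome variants descriptively.

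The cost is wording and slightly less covariate adjustment, with no new data or samples. The analysis remains exploratory: with a family of three tests, power is still only about 13-22% for an odds ratio of 3 and 25-46% for an odds ratio of 5 (adjusted likelihood-ratio tests, n = 39). The caveat on power should stay.
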